16.2 Statistical Design

- 6.21 The primary goal is to compare the OS between evaluable patients who were randomized to R+E (arm A) and E+R (arm B). The null hypothesis is that R+E (arm A) does not show a significantly superior OS outcome compared to E+R (arm B). The alternative hypothesis is that R+E has improvement in OS compared to E+R.

16.22 Power and Sample Size

We will enter 26 evaluable patients to each arm of the study using a 1:1 randomization scheme (52 evaluable patients in total), unless the study is stopped early. Stratification factors are defined in section 5.0. With 26 evaluable patients per arm, we have 80% power to detect an improvement in median OS from 7.5 months to 14.5 months, assuming a 1-sided significance level of 0.1, and exponential survival.

An additional 8 patients (4 in each arm) will be enrolled to account for ineligibility, major violation, loss of follow-up, etc. The total expected accrual for primary analysis (i.e. patients with right-sided tumor) is 60. Including the 12 patients with left-sided tumors who enrolled prior to Amendment 2, the total expected accrual is 72 patients.

16.23 Final Analysis and Decision Rules

Efficacy analysis will be conducted when at least 42 death events, across both arms combined, have been observed. If the 1-sided p-value from stratified log-rank test is > 0.1 (hazard ratio > 0.673) for arm A vs. B, (R+E) treatment regimen will be considered ineffectual. Conversely, if the 1-sided p-value from stratified log-rank test is ≤ 0.1 (hazard ratio ≤ 0.673) for Arm A vs. B, the (R+E) treatment regimen will be considered promising for future study. Evaluable patients will be used for this analysis (see 16.1 for evaluable definition). The stratified log-rank test will be used for decision making except when there are 0 events in any of the strata; in that case, the unstratified log-rank will be used for decision making.

Analysis time point	Number of events ¹	Critical p-value		Hazard Ratio	
		Futility	Efficacy	Futility	Efficacy
100%	42	> 0.1	≤ 0.1	> 0.673	≤ 0.673

16.24 Operating Characteristics

The table below shows the operating characteristics assuming the OS follows the exponential survival function along with a one-sided significance level of 0.1. The proportion of times that regorafenib followed by anti-EGFR (R+E) would be concluded to be superior at the final analysis are tabulated by true median OS times and equivalent true hazard ratios for OS by treatment groups.

True median overall survival (months) ³		True Hazard Ratio (Arm A vs. B)	% of times that R+ E is deemed superior at the final analysis ⁴
R + E ¹ (Arm A)	E + R ² (Arm B)		
7.5	7.5	1	10.3
9.5	7.5	0.789	30.0
11	7.5	0.682	47.8
12.5	7.5	0.6	63.7
14.5	7.5	0.517	79.4

¹ R + E: regorafenib followed by anti-EGFR \pm irinotecan

² E + R: anti-EGFR \pm irinotecan followed by regorafenib

³ Although we use the median OS to illustrate each scenario, the hypothesis testing is based on the entire survival curve.

⁴ Proportions are based on 50,000 replicates in a simulation study

16.25 Accrual Time and Study Duration

We plan to accrue a total of 72 patients (approximately 30 patients per arm with right-sided tumor + 12 patients enrolled with left-sided tumor) in 51 months with a minimum follow-up of 7.5 months to achieve 42 OS events. The length of accrual time is based on an accrual rate of 0.2 patients per month for the first 33 months and 3 patients per month for the remaining accrual period.

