13.0 Treatment/Follow-up Decision at Evaluation of Patient

- 13.1 A patient is deemed *ineligible* if after randomization, it is determined that at the time of randomization, the patient did not satisfy each and every eligibility criteria for study entry. The patient may continue treatment off-protocol at the discretion of the physician as long as there are no safety concerns, and the patient was properly registered. The patient will go directly to the event-monitoring phase of the study (or off study, if applicable).
- If the patient received treatment, all data up until the point of confirmation of ineligibility must be submitted. Event monitoring will be required per Section 18.0 of the protocol.
- 13.2 A patient is deemed a *major violation*, if protocol requirements regarding treatment in cycle 1 of the initial therapy are so severely violated that evaluability for the primary endpoint is questionable. All data up until the point of confirmation of a major violation must be submitted. The patient will go directly to the event-monitoring phase of the study. The patient may continue treatment off-protocol at the discretion of the physician as long as there are no safety concerns, and the patient was properly registered. Event monitoring will be required per Section 18.0 of the protocol.
- 13.3 A patient is deemed a *cancel* if he/she is removed from the study for any reason before any study treatment is given. On-study material and the End of Active Treatment/Cancel Notification Form must be submitted. No further data submission is necessary.
- 13.4 Patients who are CR, PR, or SD will continue treatment per protocol with evaluation every 8 weeks, until disease progression or intolerance.
- 13.5 Patients who develop PD while receiving therapy on the initial treatment may be re-registered to the sequential treatment phase, or may go to event-monitoring, per physician discretion. If a patient develops PD while receiving sequential treatment, they will be followed for survival (i.e. event monitoring phase) every 3 months (± 7 days) for 3 years after randomization (per Section 18.0).

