16.3 Analysis Plan

The analysis for this trial will commence when the sufficient number of OS events has been observed (see 16.23). Such a decision will be made by the Statistician and Study Chair, in accordance with CCS Standard Operating Procedures, availability of data for secondary endpoints (eg, laboratory correlates), and the level of data maturity.

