16.31 Primary Endpoint

16.311 Definition

The primary endpoint for this trial is to compare the overall survival (OS) between evaluable patients who were randomized to arm A and arm B. Overall survival is defined as the time from study entry to death from any cause. OS will be estimated using the Kaplan-Meier method and compared between treatment groups using the stratified log-rank test. The median OS and 95% confidence interval will be reported. Patients will be censored at the date patient was last known to be alive.

16.312 Over Accrual

If more than the target number of patients are accrued, the additional evaluable patients will be used for decision making.

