Lost to Follow-Up ³					At each occurrence
Notice of New Primary ³					At each occurrence
Consent Withdrawal (choose appropriate form) ³					At each occurrence
• Consent Withdrawal: Optional Specimens					
• Consent Withdrawal: All Follow-Up					
ACCRU Deviation Form ³					

1. If a patient is still alive 3 years after randomization, no further follow-up is required.
2. Attach a copy of documentation of response or progression in RAVE on the Supporting Documentation Form.
3. Submit only if applicable.
4. Please use the “Add Event” function to record the first instance of non-protocol treatment received. If the patient has never had any non-protocol treatment, record as “no” at the end of the Event Monitoring Phase.

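### Does the plan need a rule for a trial that ends with fewer than 42 deaths?

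*Combined protocol and SAP*

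**What the plan says.** Section 16.22 sets the target as a number of patients: 52 evaluable, 26 per arm, "unless the study is stopped early". Eight more bring right-sided enrolment to 60. The design has 80% power at one-sided 0.1 for medians of 7.5 versus 14.5 months.

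Section 16.23 sets the trigger: "Efficacy analysis will be conducted when at least 42 death events, across both arms combined, have been observed". The decision rests on the one-sided p-value of the stratified log-rank test against 0.1 (unstratified if a stratum has no events). A hazard ratio of 0.673 appears in parentheses and in the table beside it. Section 16.3 points back to 16.23 for the start of analysis and adds: "Such a decision will be made by the Statistician and Study Chair", with reference to standard operating procedures and data maturity.

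Section 16.25 expects enrolment "in 51 months with a minimum follow-up of 7.5 months to achieve 42 OS events", based on "an accrual rate of 0.2 patients per month for the first 33 months and 3 patients per month for the remaining accrual period".

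Sections 13.5 and 13.6 follow patients for survival "for 3 years after randomization (per Section 18.0"), and the follow-up table in 18.1 notes: "If a patient is still alive 3 years after randomization, no further follow-up is required". Section 16.312 deals with the opposite case: "If more than the target number of patients are accrued, the additional evaluable patients will be used for decision making".

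**The concern.** The trigger is a death count, while required follow-up for each patient ends at 36 months, so deaths cannot be relied on to accumulate indefinitely. Nearly all right-sided enrolment depends on the later accrual rate. If accrual stopped early or patients lived longer than assumed, the trial could end below 42 with no written time or rule for its primary analysis. Section 16.312 covers only over-accrual, and 16.22 and 16.26 allow early stopping without saying how the data would then be analysed.

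The choice would fall to the Statistician and Study Chair, who under 16.41 also review the study for endpoint problems at least twice a year. In addition, the two boundaries printed in 16.23 agree only at 42 deaths. Below that, a result could pass on the hazard ratio and fail on the p-value. Section 16.25 also names neither the survival scenario nor the evaluable number behind its forecast.

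**Working it through.** **1. The plan's own figures.**
- Deaths for 80% power, one-sided 0.1, 1:1 (Schoenfeld): 4 × (1.2816 + 0.8416)² / [ln(14.5/7.5)]² = 41.5, so 42.
- Critical hazard ratio at 42 deaths: exp(−2 × 1.2816/√42) = 0.673.
- Accrual: 33 × 0.2 + 18 × 3 = 6.6 + 54 = 60.6, matching the 60 right-sided patients.

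All three agree with 16.22, 16.23 and 16.25.

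**2. Can 42 be reached within 3 years per patient?** The probability of death by 36 months is 1 − 0.5^(36/median):
- 14.5 months: 0.8211; 7.5 months: 0.9641; 1:1 average 0.8926.
- Patients needed to expect 42 deaths: 42/0.8926 = 47.05, against 52 planned.

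The chance of fewer than 42 deaths, from the exact sum of two binomials with complete follow-up to 36 months, is:

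| Evaluable | 14.5 vs 7.5 | 7.5 vs 7.5 | 17.4 vs 11.6 |
|---|---|---|---|
| 48 | 24.9% | 0.2% | 77.5% |
| 50 | 7.7% | <0.1% | 53.9% |
| 52 | 1.8% | <0.1% | 30.9% |
| 56 | <0.1% | <0.1% | 5.8% |
| 60 | <0.1% | <0.1% | 0.6% |

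The last column uses the medians of the Japanese trial cited in 1.9, not the design medians.

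**3. Loss to follow-up (assumed rates; none is given).** In simulation under the alternative, loss of 0.5%, 1% and 2% per month gives a chance of reaching 42 of about 83%, 55% and 11% with 52 evaluable, and 99.9%, 98% and 73% with 60. By the definition in 16.1, an eligible treated patient who is later lost still counts as evaluable. Since the eight extra patients in 16.22 are partly for such losses, the 60-patient figures are the closer guide when loss is modelled separately.

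**4. Slower accrual.** If the later rate were 2 per month and accrual closed at month 51, there would be 33 × 0.2 + 18 × 2 = 42.6 right-sided patients and at most 42.6 × 0.8926 = 38.0 expected deaths. At 2.5 per month: 51.6 × 52/60 = 44.7 evaluable and 39.9 expected deaths. Both need closure at month 51. Section 16.25 gives 51 months as a plan, whereas 16.22 fixes the number of patients. If accrual continued, 60 would be reached at 33 + 53.4/2 = month 59.7 or 33 + 53.4/2.5 = month 54.4. The result is delay, not a missed trigger.

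**5. Effect of the 3-year limit.** Under the alternative, the median time of the 42nd death after last enrolment is 8.6 months with the limit and 8.4 without it (60 evaluable), or 15.7 and 15.2 (52 evaluable).

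**6. The decision below 42 deaths.** The boundary equivalent to p = 0.1 is exp(−2 × 1.2816/√D). The error from using 0.673 alone is 1 − Φ(0.396 × √D/2), where 0.396 = −ln 0.673. Power is Φ(ln(14.5/7.5) × √D/2 − 1.2816).

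| Deaths | HR equivalent to p = 0.1 | Error if HR ≤ 0.673 used alone | Power of the p-value rule |
|---|---|---|---|
| 42 | 0.673 | 10.0% | 80.4% |
| 38 | 0.660 | 11.1% | 77.3% |
| 35 | 0.648 | 12.1% | 74.8% |
| 30 | 0.626 | 13.9% | 70.0% |

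The third column arises only if the stated test is abandoned. The log-rank rule stays at a nominal 10% throughout.

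**7. The duration forecast.** With 60 evaluable and the 16.25 accrual rates, expected deaths at month 58.5 (no 3-year limit) are 46.8, 44.6, 43.1, 41.9 and 40.4 for the five arm A medians in 16.24. The forecast is met or nearly met in four and is 1.6 short under the alternative. With 52 evaluable, about 35 are expected under the alternative. Because the trigger is a count of deaths, this moves only the calendar date.

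**The case for a change.** The best case for a change is that it would cost a sentence or two and add no patients or visits, while removing discretion from people who see the accumulating data. About 89% of right-sided enrolment (54 of 60.6) rests on a rate 15 times the earlier one, so a shortfall is not fanciful. With the medians of the trial that this study sets out to confirm, the chance of missing 42 is 30.9% at 52 evaluable even with full accrual and complete follow-up.

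Part of this stands: no visible text gives a rule for ending below 42. The rest is weaker. The 30.9% replaces the plan's control median of 7.5 months with medians from a trial that 1.9 does not describe as limited to right-sided disease, and it falls to 5.8% with 56 evaluable and 0.6% with 60. The discretion concerns timing; the test and its level are already fixed in 16.23. A safety monitoring board also reviews accrual at least twice a year (16.41). Finally, 18.1 says that follow-up beyond 3 years is not required; it does not exclude a later death that becomes known.

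**Conclusion.** No change is needed. The printed figures are right, and the plan lacks only a contingency clause. Followed as written, with 52 evaluable patients, the design medians, exponential survival and complete follow-up to 3 years, it reaches 42 deaths with about 98% probability; with 56 or more, failure is below 0.1%. If it did end short, analysts would sensibly run the same stratified log-rank test at one-sided 0.1 on the deaths available. That rule keeps its level, and power at 35 deaths would be about 75%. Naming a scenario in 16.25 would relabel a forecast without altering any result.

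The conclusion depends on enrolment continuing to the target in 16.22 and on modest loss to follow-up. It would weaken if accrual closed well short of 52 evaluable patients or survival ran much longer than assumed. Two items could not be seen: the footnote to the event count in the 16.23 table, whose text is absent from our copy, and the operating procedures cited in 16.3. Either may already address the point.

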16.26 Other Considerations

Adverse events, quality/duration of response, and patterns of treatment failure observed in this study, as well as scientific discoveries or changes in standard care will be taken into account in any decision to terminate the study.

16.3 Analysis Plan

The analysis for this trial will commence when the sufficient number of OS events has been observed (see 16.23). Such a decision will be made by the Statistician and Study Chair, in accordance with CCS Standard Operating Procedures, availability of data for secondary endpoints (eg, laboratory correlates), and the level of data maturity.

16.31 Primary Endpoint

16.311 Definition

The primary endpoint for this trial is to compare the overall survival (OS) between evaluable patients who were randomized to arm A and arm B. Overall survival is defined as the time from study entry to death from any cause. OS will be estimated using the Kaplan-Meier method and compared between treatment groups using the stratified log-rank test. The median OS and 95% confidence interval will be reported. Patients will be censored at the date patient was last known to be alive.

16.312 Over Accrual

If more than the target number of patients are accrued, the additional evaluable patients will be used for decision making.

16.32 Secondary Endpoints

16.321 First Progression-Free Survival (PFS1)

Progression-free survival one (PFS1) is defined as the time interval between randomization date and the date of first progression while on initial treatment or until death whichever is first, where disease progression will be determined based on RECIST 1.1 criteria. PFS will be estimated using the Kaplan-Meier method and compared between groups using the log-rank test. The median PFS and 95%

confidence interval will be reported. Patients with no defined events observed during the follow-up period will be censored at the last disease assessment date prior to the initiation of sequential treatment, if applicable.

16.322 Second Progression-Free survival (PFS2)

Second progression-free survival (PFS2) is defined as the time interval from re-registration to the sequential treatment phase until the date of progression while on sequential treatment or until death, whichever occurred first. Disease progression will be determined based on RECIST 1.1 criteria. PFS2 will be estimated using the Kaplan-Meier method and compared between groups using the log-rank test. The median PFS2 and 95% confidence interval will be reported. Patients will be censored at the last disease assessment date while on sequential treatment .

16.323 Sequential Treatment Progression-Free Survival (stPFS)

Sequential treatment progression-free survival is defined as the time from randomization until progression while on the sequential treatment or until death, whichever occurred first. Patients who did not experience an event during follow-up will be censored at the last disease assessment date.

Patients who completed initial treatment but did not begin sequential treatment will be censored at the date of last disease evaluation prior to discontinuation of initial treatment. Patients who began sequential treatment but discontinued protocol treatment prior to progression will be censored at the last disease assessment date while on sequential treatment. Analysis methods will mirror those of the other PFS endpoints.

16.324 Objective Response Rate

The objective response rate to initial treatment will be estimated by the number of patients who achieve a best response to initial treatment of complete response or partial response (CR or PR) divided by the total number of evaluable patients. Point estimates and the corresponding 95% confidence intervals for the true success proportions will be calculated.

16.325 Sequential Treatment Objective Response Rate

The objective response rate to sequential treatment is defined as the number of patients who achieve a best response to sequential treatment of complete response or partial response (CR or PR) while on sequential treatment divided by the total number of evaluable patients who initiated sequential treatment. Point estimates and the corresponding 95% confidence intervals for the true success proportions will be calculated.

16.326 Adverse Events

Adverse events by patient will be summarized by frequencies and severity using CTCAE version 5.0. We will also closely monitor adverse events throughout the study.

16.327 Correlative Research

Serial blood collections – prior to cycle 1, every 8 weeks at the time of restaging scans and disease progression will be collected to post-hoc evaluate for plasma biomarkers prognostic or predictive to response and acquired treatment resistance

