6.3 Randomization Procedures

6.31 The factors, defined in Section 5.0, together with the registering membership, will be used as stratification factors.

6.32 After the patient has been registered into the study, the values of the stratification factors will be recorded, and the patient will be assigned to one of the two treatment groups using the Pocock and Simon [39] dynamic allocation procedure which balances the marginal distributions of the stratification factors between the treatment groups. At entry, physicians must declare whether each patient will receive irinotecan in protocol treatment (ie, irinotecan+anti-EGFR therapy versus anti-EGFR therapy alone). The stratification factors is defined as 6.21.

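### PFS1 and stPFS are given a plain log-rank test although OS is stratified and allocation is balanced on the same factors: a minor, cheap improvement

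*Combined protocol and SAP*

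**What the plan says.** - **OS.** Section 16.311 has OS "compared between treatment groups using the stratified log-rank test". Section 16.23 repeats this for the decision rule and adds an exception: "The stratified log-rank test will be used for decision making except when there are 0 events in any of the strata". Where that happens, the plan switches to a test that it expressly calls unstratified.
- **PFS1 (16.321).** "PFS will be estimated using the Kaplan-Meier method and compared between groups using the log-rank test". Stratification is not mentioned.
- **PFS2 (16.322).** "PFS2 will be estimated using the Kaplan-Meier method and compared between groups using the log-rank test". Its clock is the "time interval from re-registration to the sequential treatment phase until the date of progression while on sequential treatment", or death.
- **stPFS (16.323).** Measured from randomisation. "Analysis methods will mirror those of the other PFS endpoints".
- **Allocation (5.1, 6.31, 6.32).** The two stratification factors are prior bevacizumab in the metastatic setting and the physician's decision on irinotecan with the antibody, both yes/no. Section 6.31 adds the registering membership. The Pocock-Simon procedure "balances the marginal distributions of the stratification factors between the treatment groups".
- **Strata of the OS test.** Neither 16.23 nor 16.311 lists them. Section 16.22 only points to Section 5.0, which also holds a grouping factor (initial treatment received).

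**The concern.** The plan uses stratified and unstratified as distinct terms in 16.23, so an unqualified log-rank test in 16.321 is most naturally taken as unstratified. No reason is given for treating PFS1 and stPFS differently from OS, although all three start at randomisation under the same balanced allocation.

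Balancing on a prognostic factor makes the arms more alike than simple randomisation would. An unstratified log-rank test ignores this, so its variance is too large for the design: it rejects too seldom under the null and gives up power. The silence also leaves the choice of test open until the data are in hand. At stake is the sensitivity of two secondary comparisons and their consistency with OS, not the trial's decision.

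**Working it through.** **1. The plan's own figures (OS).** Inputs from 16.22 and 16.23: medians 7.5 and 14.5 months, one-sided alpha 0.1, 80% power, 1:1 allocation, 42 deaths.

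- HR = 7.5/14.5 = 0.517.
- Schoenfeld events = 4(1.282 + 0.842)²/(ln 0.517)² = 18.0/0.435 ≈ 41.5, so 42.
- Power at 42 events = Φ(0.659 × √42/2 − 1.282) = Φ(0.854) = 80.4%. The plan states 80%, and 79.4% by simulation in 16.24.
- Critical HR = exp(−2 × 1.282/√42) = 0.673, as stated.

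The OS design reproduces with an unstratified formula. No event count, effect size, alpha or power is stated for any PFS endpoint, so there is no PFS figure to reproduce.

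**2. Illustration on the OS design.** 8,000 replicates per scenario, 52 patients, analysis at 42 events, one-sided 0.1, true HR 1 or 0.517. Assumed: minimisation on two binary factors (membership left out) with biased coin 0.8, uniform accrual over 18 months, factor prevalences 50/50 or 80/60, and factor effects equal in both arms. Ranges span the two prevalence settings. Monte Carlo standard error is about √(0.1 × 0.9/8000) = 0.3 points for type I error and √(0.75 × 0.25/8000) = 0.5 points for power.

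| HR of each factor | Type I, unstratified | Type I, stratified | Power, unstratified | Power, stratified |
|---|---|---|---|---|
| 1.0 | 10.1–10.3% | 10.0–10.2% | 78.6–78.8% | 75.5% |
| 1.5 | 9.1–9.6% | 9.8–10.2% | 77.0–77.3% | 75.1–75.9% |
| 2.0 | 8.1–9.1% | 9.8–10.3% | 72.8–73.4% | 75.2–75.9% |
| 3.0 | 6.6–7.4% | 10.0–10.5% | 64.2–65.8% | 74.7–76.0% |

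Stratifying loses about 3 points of power at factor HR 1 and 1 to 2 points at 1.5. It gains about 2 points at 2 and about 10 at 3. The zero-event fallback was triggered in 0 to 23% of simulated trials. With it, power was 73.2–76.0% across all scenarios; at factor HR 3 with 80/60 prevalences the gain is then 73.2 − 65.8 = 7.4 points.

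**3. A PFS1-like setting.** 10,000 replicates, 52 patients balanced within four strata, about 50 events. Assumed: control median 3 months, true HR 0.6, and the one-sided 0.1 level borrowed from OS.

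- Factor HR 2 each: unstratified 62.1% power and 9.1% type I error; stratified 64.4% and 10.1%.
- Factor HR 3 each: 56.9% and 8.3%, against 64.2% and 10.5%.
- Factors not prognostic: power 67.2% unstratified, 63.5% stratified.

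**4. How strong might the irinotecan factor be?** Section 1.1 cites a randomised phase II study of cetuximab with or without irinotecan, with PFS of 4.1 against 1.5 months. Under exponential PFS that is a ratio of 4.1/1.5 = 2.7. It is an effect of giving irinotecan, not of planning to give it.

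- For stPFS, both arms receive the antibody regimen at some stage. With irinotecan HR 2.7 in both arms, no bevacizumab effect and treatment HR 0.6 (6,000 replicates), type I error was 7.9–8.6% unstratified and 10.1% stratified; power was 60–62% and 64–65%. With neither factor prognostic, power was 69–70% and 64–65%.
- For PFS1, Arm A receives regorafenib alone (Section 7.0), so the regimen effect falls in Arm B only. With irinotecan HR 0.67 in Arm B only and bevacizumab HR 1 to 2 (6,000 replicates), stratifying changed power by −1 to +2 points. With HR 0.5 it gained 1 to 4.

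**The case against.** A fair defence is that a plain log-rank test is a legitimate choice for secondary endpoints with 52 patients in four cells, and that 16.23 itself reverts to it for OS when a stratum has no events. The benefit of stratifying rests on prognostic strengths and prevalences that the documents do not give. At factor HR 1.5 there is no gain, and the loss with uninformative factors exceeds the gain at factor HR 2. This stands, and it keeps the point minor. It does not explain why OS is handled differently, or why the choice is left unstated.

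A reader might go further in four ways that the documents do not support:

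- **That PFS false positives are inflated.** The simulations show the opposite: the unstratified test is conservative when the factors matter. The 0.1 threshold and the go/no-go rule belong to OS only.
- **That the plan expressly chooses an unstratified PFS test.** Section 16.32 never uses that word. It is the likelier reading, but still an inference.
- **That irinotecan changes the regimen in both arms for PFS1.** It does so for stPFS; in PFS1 it acts in Arm B alone. The planned choice may also mark fitness, but no figure is given for that.
- **That stratifying would repair PFS2.** PFS2 starts at re-registration, among patients who reach sequential treatment. Stratifying would not restore a randomised comparison.

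**Conclusion.** The point holds as a minor improvement. OS is tested with stratification, while PFS1 and stPFS, which also start at randomisation, are not stated to be. Under assumed factor hazard ratios of 2 to 3 each, acting in both arms, an unstratified test has a one-sided type I error of about 7–9% against a nominal 10% and gives up about 2 to 10 points of power. With weaker factors there is little or no gain, and with uninformative ones stratifying costs about 3–5 points. All of these figures are illustrative: they rest on assumed factor strengths and prevalences and on the OS alpha. The case is stronger for stPFS than for PFS1. No stated figure and no trial decision changes.

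**What to change.** - In 16.321 and 16.323, specify the log-rank test stratified by the two Section 5.1 factors (prior bevacizumab, planned irinotecan). Carry over the 16.23 rule: if any stratum has no events for that endpoint, use the unstratified test.
- Report a Cox hazard ratio for PFS1 and stPFS, stratified in the same way.
- Name the same two factors as the strata of the OS test in 16.23 and 16.311, and say that registering membership is used for allocation only.
- Leave 16.322 (PFS2) out of this change.
- If the sponsor prefers the unstratified test for PFS, say so and give the reason.

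The cost is a few lines of analysis-plan text, settled before the PFS data are analysed, and a possible loss of about 3–5 points of PFS power if the factors prove uninformative.
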